10.2 ADVERSE EVENTS

Each AE and serious adverse event (SAE) term recorded on the case report forms (CRFs) by primary system organ class (SOC) will be mapped to a preferred term using the MedDRA dictionary. The investigator will assess AE severity and relationship to the study treatment.

A treatment emergent adverse event (TEAE) is defined as any AE that occurs within the TEAE window. This window starts on the randomization date and ends 7 days after the last dosing date for non-serious AEs and 30 days after the last dosing for SAEs. All AEs that are considered by the Investigator as treatment related will be treated as TEAEs. Only TEAEs will be summarized in tables (unless otherwise stated AEs in tables are TEAEs). However, all AEs recorded will be listed. For the purpose of calculating treatment emergence and inclusion in summary tables, incomplete onset dates will be imputed as detailed in [Appendix B](#).

AEs will be summarized by the number and percent of subjects in each primary SOC and preferred term. Patients will be counted only once for each primary SOC and each preferred term. Summary tables of AEs by primary SOC, preferred term and severity will be provided. If a subject has more than one AE coded to the same preferred term, the subject will be counted only once for that preferred term by using the event with the highest severity. Similarly, if a subject has more than one AE within a primary SOC category, the subject will be counted only once in that SOC category by using the event with the highest severity. AEs by primary SOC, preferred term and relationship to study drug will be provided as well. If a subject has more than one AE coded to the same preferred term, the subject will be counted only once for that preferred term by using the most related event. Similarly, if a subject has more than one AE within a primary SOC category, the subject will be counted only once in that primary SOC category by using the most related event. In addition, SAEs by primary SOC and preferred term will be provided. Deaths and SAEs will be summarized similarly to AEs. All adverse event tables will also include the total number of events, counting multiple events per patient.

In the AE summary, preferred terms within each SOC will appear in alphabetical order.

Frequencies for deaths and hospitalizations will also be summarized by treatment group and overall.

Other safety analyses will be performed as appropriate

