14.2 APPENDIX B - IMPUTATION ALGORITHM FOR PARTIAL AND MISSING DATES

This section describes missing date imputation methods.

For Adverse Events

If onset date is completely missing, onset date is set to date of randomization.

If (year is present and month and day are missing) or (year and day are present and month is missing):

- If year = year of randomization, then set month and day to month and day of randomization
- If year < year of randomization, then set month and day to December 31.
- If year > year of randomization, then set month and day to January 1.

If month and year are present and day is missing:

- If year=year of randomization and
 - If month = month of randomization then set day to day of first dose
 - If month < month of first dose then set day to last day of month
 - If month > month of first dose then set day to first day of month
- If year < year of randomization then set day to last day of month
- If year > year of randomization then set day to first day of month

For all other cases, set onset date to date of randomization.

For Concomitant Medications

Start Date: If start date is completely missing and end date is not prior to randomization, then the medication will be classified as concomitant. If start date is completely missing and end date is prior to randomization, then the medication will be classified as prior.

If (year is present and month and day are missing) or (year and day are present and month is missing) then set month and day to January 1. If year and month are present and day is missing then set day to first day of month.

End Date: If end date is completely missing then the medication will be classified as concomitant.

If (year is present and month and day are missing) or (year and day are present and month is missing) then set month and day to December 31. If year and month are present and day is missing then set day to last day of the month.

Note: that if both start and end dates are missing then the medication will be classified as concomitant.

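### Appendix B imputes incomplete AE onset dates without looking at the end date, so an event known to have ended before randomization can be tabulated as treatment-emergent

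*SAP*

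**What the plan says.** The adverse event part of SAP Appendix B (section 14.2) has four branches that can place an incomplete onset at or after randomization:

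- Nothing known: "If onset date is completely missing, onset date is set to date of randomization".
- Month missing, year known: "If year = year of randomization, then set month and day to month and day of randomization".
- Day missing, month and year known, in the randomization year: "If month = month of randomization then set day to day of first dose".
- Anything left over: "For all other cases, set onset date to date of randomization".

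None of the four refers to the date on which the event ended.

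SAP section 10.2 makes these dates matter: "For the purpose of calculating treatment emergence and inclusion in summary tables, incomplete onset dates will be imputed as detailed in" Appendix B. It also sets the window: "This window starts on the randomization date and ends 7 days after the last dosing date for non-serious AEs", with a longer tail for serious events. Separately, any event that the investigator judges related counts as treatment-emergent whatever its timing. SAP section 10.0 assigns each event to whichever treatment the subject took most recently.

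The medication part of the same appendix does consult the end date when the start is unknown: "If start date is completely missing and end date is prior to randomization, then the medication will be classified as prior".

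**The concern.** Moving an unknown onset towards treatment emergence is a normal conservative choice when nothing else is known about timing. It stops being conservative when the record already shows that the event was over before randomization. The four branches then override a known fact with a default. The event enters the treatment-emergent tables, and the analysis dataset holds an onset later than the end.

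At stake is the accuracy of the adverse event incidence tables in a trial of about 20 subjects, where one subject visibly moves a percentage. If first dose is on the day of randomization, the rule in section 10.0 would most naturally assign such an event to the Period 1 treatment, although the subject had taken neither treatment when it ended. Efficacy results are not touched.

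**Working it through.** The plan states no figure to reproduce. The check is to run the rules as written on example records.

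**Inputs from the documents.** The Appendix B branches and the section 10.2 window, as above. First dose is given in clinic on Day 1, Visit 2 (SAP section 4.3). The calendar day of randomization is not stated separately. Planned size is about 20 subjects (protocol synopsis; SAP section 9.5).

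**Assumed for illustration.** Randomization on 17 June 2019; first dose the same day or one day later; event ended on 10 June 2019, which is 7 days before randomization.

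**Rule applied.** An event is treatment-emergent if randomization date ≤ imputed onset ≤ last dose + 7 days (non-serious). The proposed check adds: not treatment-emergent if the event is known to have ended before randomization.

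| Onset as recorded | End | Imputed onset | Treatment-emergent as written | Onset minus end | With the check |
|---|---|---|---|---|---|
| Completely missing | 10 June | 17 June | Yes | 17 − 10 = 7 days | No |
| 2019 only | 10 June | 17 June | Yes | 7 days | No |
| June 2019, day missing | 10 June | 17 or 18 June | Yes | 7 or 8 days | No |
| May 2019, day missing | 10 June | 31 May | No | onset precedes end | No |
| Completely missing | 17 June | 17 June | Yes | 0 days | Yes |
| Completely missing | 17 July | 17 June | Yes | onset precedes end | Yes |

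The catch-all branch was not run separately. It assigns the randomization date, so it behaves like the first row.

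The first three rows show the defect. The window includes its first day, so any onset set to the randomization date is inside it by construction. The June row also lands inside, because first dose is on or after randomization and here falls in the same calendar month. The last two rows show that the check leaves alone events that ended on or after randomization.

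**Size.** Section 10.2 counts a subject once per preferred term. One misclassified subject who does not otherwise have that term on that treatment changes its incidence by 1/20 = 0.05, or 5 percentage points, taking about 20 subjects as the denominator for each treatment. Two such subjects give 2/20 = 10 points, but only if they share both the preferred term and the treatment. A subject who also has the term genuinely on that treatment adds 0 points to incidence.

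**The case against.** The best case for the plan is that this will rarely or never matter. Three things must coincide: a screening-phase event is recorded, its onset is incomplete in the relevant part, and its end is known to precede randomization. Neither the SAP nor the protocol synopsis says when event recording starts. SAP section 12.0 provides for source verification and for electronic and manual checks, which make an end date without an onset date less likely. All recorded events are listed in any case, and section 10.0 makes any formal safety comparison post hoc. These points stand. They limit the size of the problem, but they do not make the rule correct when it is triggered.

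The contrast with the medication rule is only supporting evidence. SAP section 8.0 defines a prior medication by its stop date, so that rule has to use the end date, whereas treatment emergence depends on when the event occurs. The contrast shows that an end-date check was within reach, not that the two halves of the appendix had to match.

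A reader might infer four stronger things that the documents do not support:

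- *That such events are likely*, because exclusion criterion 3 requires several drug classes to be withdrawn before treatment. Washout makes screening symptoms plausible. It says nothing about missing onset dates.
- *That the rule favours one treatment.* It ignores treatment, and sequence is randomized 1:1, so no systematic difference between treatments is expected.
- *That the error reaches 1/10 = 10 points within a sequence.* SAP section 10.2 plans no adverse event table by sequence.
- *That any event ending before first dose gets an onset after its own end.* For a date set to randomization, the contradiction requires an end before randomization. An event ending between randomization and first dose is already inside the SAP's window.

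**Conclusion.** The point holds as a narrow defect in a stated rule. An adverse event recorded as ended before randomization, with an onset that is completely missing, year-only in the randomization year, day-missing in the randomization month, or in the catch-all, is counted as treatment-emergent with an onset after its own end. No other part of the SAP or the protocol synopsis overrides this.

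The size is about 5 percentage points in one preferred term per affected subject, under the conditions given in the working. The number of affected subjects is unknown and may be zero. Attribution to the Period 1 treatment assumes that first dose is on the day of randomization. The day-missing branch assumes that both dates fall in the same calendar month. The consequence is confined to safety tables, so this is a minor correction, worth making because it is so cheap.

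**What to change.** Add to the adverse event part of Appendix B:

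> If the AE end date, or the known parts of it, establish that the event ended before the randomization date, the AE is not treatment-emergent, unless the Investigator considers it treatment related (section 10.2). Where a complete end date is available, the imputed onset may not be later than the end date. If the end date is missing or its known parts do not establish that the event ended before randomization, the existing rules apply.

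The check is tied to randomization, not first dose, so that it leaves the treatment-emergent window of section 10.2 unchanged. The exception preserves that section's rule on related events. A partial end date acts only when it settles the matter, so no end-date imputation is needed.

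The cost is a short addition to Appendix B and a small change to the date-imputation program. No new data are needed.

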1. SYNOPSIS

| | |
|---------------------|--|
| PRODUCT NAME/NUMBER | AXS-12 (reboxetine) |
| PROTOCOL NUMBER | AXS-12-201 |
| PROTOCOL TITLE | A Multi-center, Randomized, Double-blind, Placebo-controlled, 3-Week Crossover Study to Assess the Efficacy and Safety of AXS-12 in Subjects with Cataplexy and Excessive Daytime Sleepiness in Narcolepsy |
| INDICATION | Treatment of Cataplexy in Narcolepsy |
| DEVELOPMENT PHASE | Phase 2 |
| OBJECTIVES | 
Primary Objective: To assess the effect of AXS-12 as compared to placebo on the number of cataplexy attacks as recorded in a Sleep and Symptom Daily Diary.
 
Secondary Objectives: To assess the effect of AXS-12 on:
 
 - Patient Global Impression of Severity (PGI-S) - Hamilton Rating Scale for Depression (HAM-D) - Epworth Sleepiness Scale (ESS) - Narcolepsy Symptom Assessment Questionnaire (NSAQ) - Ability to Concentrate item of the NASQ |
| STUDY DESIGN | 
This study is a three-week, crossover, multi-center, randomized, double-blind, placebo-controlled proof-of-concept Phase 2 trial to assess the safety and efficacy of AXS-12 in narcoleptic subjects with cataplexy and excessive daytime sleepiness (EDS). Eligible subjects must have a diagnosis of narcolepsy per the International Classification of Sleep Disorders, Third Edition (ICSD-3) criteria, and exhibit symptoms of both cataplexy and EDS. Subjects meeting the entry criteria will be randomized in a 1:1 ratio either to placebo for three weeks followed by AXS-12 (up to 10 mg daily) for three weeks, or to AXS-12 (up to 10 mg daily) for three weeks followed by placebo for three weeks. Study medication will be down-titrated during the third week of each three-week treatment period.
 
The primary endpoint will be the change in the number of cataplexy attacks as recorded in a Sleep and Symptom Daily Diary. Secondary outcome measures will include the Maintenance of Wakefulness Test (MWT), Patient Global Impression of Severity (PGI-S), Epworth Sleepiness Scale (ESS), Hamilton Rating Scale for Depression (HAM-D), Narcolepsy Symptom Assessment Questionnaire (NSAQ), and the Ability to Concentrate item of the NASQ.
 
Screening Period
 
All subjects will enter an up to three-week screening period (Screening, Visit 1) to determine eligibility. The screening period may last across multiple days / visits. During the screening period, an all-night polysomnography (PSG) followed by multiple sleep latency test (MSLT) may be required to confirm eligibility. Longer screening periods may be allowed to ensure washout of prior cataplexy medications.
 
Treatment Periods
 
Subjects meeting the entry criteria will be randomized in a 1:1 ratio either to placebo for three weeks followed by AXS-12 (up to 10 mg daily) for three weeks, or to AXS-12 (up to 10 mg daily) for three weeks followed by placebo for three weeks. Study medication will be down-titrated during the third week of each three-week treatment period.
 
Doses will be titrated to a target dose of 10 mg [REDACTED] during
 |

[figure not shown]
each treatment period. [REDACTED] Subjects will be monitored for safety and tolerability at each titration step.

[REDACTED] Reboxetine tablets will be over-encapsulated for blinding purposes. All study medication will be of similar appearance in order to maintain the integrity of the blind.

Assessments and Visits

On Day 1 (Visit 2) eligible subjects will undergo baseline assessments and administration of the first dose of study drug in clinic. Subsequent study visits will occur on Days 15, 22, 36, and 42 (Visits 3-6). Study procedures and assessments will be performed during study visits as outlined in the Schedule of Assessments.

Study Design Schematic

PLANNED NUMBER OF SUBJECTS

Approximately 20 subjects will be enrolled in this study.

STUDY CENTERS

Up to 10 study sites in the United States and Australia.

STUDY ENTRY CRITERIA

Inclusion criteria:

A subject will be eligible for entry into the study if all of the following inclusion criteria are met:

1. Is male or female between 18 and 70 years of age, inclusive.
2. A primary diagnosis of narcolepsy with cataplexy that meets International Classification of Sleep Disorders, Third Edition (ICSD-3) criteria determined, in part, by an overnight PSG and next-day MSLT with 2 or more sleep-onset rapid eye movement (REM) periods (SOREMPs) with mean sleep latency in the pathological range (i.e. < 8 minutes). Documentation of narcolepsy with cataplexy by PSG and MSLT within 10 years of Screening is acceptable for confirmation of diagnosis.
3. Current continuing presence of EDS as defined by subject report for the last 3 months and an Epworth Sleepiness Scale (ESS) > 10 at Screening and Baseline.
4. Documented minimum of 7 cataplexy attacks per week (or 14 across two weeks) as recorded in the subject's daily diary during the Screening period.
5. If female and of childbearing potential, is nonlactating and nonpregnant (has negative pregnancy test results at Screening and Baseline).
6. If female, is either not of childbearing potential (defined as postmenopausal for at least 1 year or surgically sterile [bilateral tubal ligation, bilateral oophorectomy, or hysterectomy]) or practicing one or more of the following medically acceptable methods of birth control:

- Hormonal methods such as oral, implantable, injectable, vaginal ring, or transdermal contraceptives for a minimum of 1 full cycle (based on the subject's usual menstrual cycle period) before study drug administration.
 - Total abstinence from sexual intercourse since the last menses before study drug administration, abstinence is acceptable when it is in line with the subject's preferred and usual lifestyle.
 - Intrauterine device.
 - Vasectomized partner.
 - Double-barrier method (condoms, sponge, or diaphragm with spermicidal jellies or cream).
7. Is willing and able to attend study visits, including overnight sleep stays, comply with study drug dosing, complete the daily cataplexy diary and all other study-related assessments.
 8. Is able to provide written informed consent to participate in the study and able to understand the procedures and study requirements.
 9. Is willing to voluntarily sign and date an informed consent form that is approved by a human research ethics committee before the conduct of any study procedure.

Exclusion criteria:

A subject will not be eligible for study entry if any of the following exclusion criteria are met:

1. Current or prior use of reboxetine.
2. Concomitant sleep disorder. Subjects with untreated mild sleep apnea (< 15 events per hour) are allowed. Subjects receiving treatment for mild to moderate sleep apnea (< 30 events per hour) are allowed if the subject is receiving stable treatment.
3. Concurrent use of any of the following medications: sodium oxybate, stimulants, anticonvulsants, clonidine, selective serotonin reuptake inhibitors (SSRIs), serotonin and norepinephrine re-uptake inhibitors (SNRIs), monoamine oxidase inhibitors (MAOIs), tricyclic antidepressants (TCAs), hypnotics, anxiolytics, sedating antihistamines, antipsychotics, or any other experimental medications designed to treat narcolepsy, cataplexy or any other condition. A longer screening period will be allowed, as needed, to ensure subjects have withdrawn any of the above medications for at least 5 half-lives, or 5 days, whichever is longer. Note: Modafinil and armodafinil are allowed provided the dose is stable for at least 3 weeks before treatment start and maintained through the study duration.
4. History of seizure or other convulsive disorder.
5. Diagnosis of cancer (other than basal cell carcinoma) within the last 5 years. Subjects who have received definitive treatment, such as curative surgery more than 6 months ago, with no known recurrence may be included following consultation with the Sponsor.
6. Bilirubin, alanine aminotransferase, aspartate aminotransferase, or alkaline phosphatase levels >2 times the upper limit of normal.
7. Clinically significant hypertension (as defined by the PI), uncontrolled hypertension, or a history of cardiovascular disease (e.g., myocardial infarction, angina, dysrhythmias, cardiac failure).
8. Current sign or symptom of severe and/or progressive or uncontrolled: hepatic, renal, gastrointestinal, endocrine, hematological, pulmonary, or neurological disease.
9. Clinically significant psychiatric disorder (eg, schizophrenia, bipolar disorder, or panic disorder) including a lifetime history of manic or psychotic episodes or who are at significant risk of self-injury, suicide, or aggression towards others. Significant risk of suicide is determined by the subject responding "yes" to question 4 or question 5 on the screening C-SSRS at Visit 1 or Visit 2, and the most recent episode occurred in the last 12 months.
10. History of narrow angle glaucoma.
11. Any other clinically significant medical condition or clinical laboratory abnormality that would in the investigator's judgment interfere with the subject's ability to participate in the study.
12. Gastric bypass or any condition that would be expected to affect drug absorption (lap band procedures are acceptable if there is no problem with absorption).
13. History of intolerance, allergy, or hypersensitivity to reboxetine or any other ingredient in the study medication.
14. Has a known or suspected history of alcoholism or drug abuse or misuse within 6 months of Screening.
15. Previously participated in another clinical study or received any investigational drug or device or investigational therapy within 30 days or 5 half-lives, whichever is longer, of Baseline.

| | |
|---|---|
| 
TEST PRODUCT, DOSAGE AND MODE OF ADMINISTRATION
 | 
Reboxetine [REDACTED] tablet, oral administration, twice daily [REDACTED] [REDACTED] Tablets will be over-encapsulated for blinding purposes.
 |
| 
REFERENCE PRODUCT, DOSAGE AND MODE OF ADMINISTRATION
 | 
Matching placebo capsules, oral
 |
| 
TREATMENT REGIMENS
 | 
Sequence 1: Period 1 (AXS-12)
 
 • Week 1 (Day 1 – Day 7): [REDACTED] over-encapsulated reboxetine tablet in the morning and [REDACTED] over-encapsulated reboxetine tablet in the afternoon. • Week 2 (Day 8 – Day 14): If tolerated, increase dose to [REDACTED] over-encapsulated reboxetine tablets in the morning and [REDACTED] over-encapsulated reboxetine tablet in the afternoon. • Week 3 (Day 15 – Day 17): [REDACTED] over-encapsulated reboxetine tablet in the morning • Week 3 (Day 18 – Day 21): No treatment 
Period 2 (Placebo):
 
 • Week 4 (Day 22 – Day 28): One placebo capsule in the morning and one placebo capsule in the afternoon • Week 5 (Day 29 – Day 35): If tolerated, increase dose to two placebo capsules in the morning and one placebo capsule in the afternoon • Week 6 (Day 36 – Day 38): One placebo capsule in the morning • Week 6 (Day 39 – 42): No treatment 
Sequence 2: Period 1 (Placebo)
 
 • Week 1 (Day 1 – Day 7): One placebo capsule in the morning and one placebo capsule in the afternoon • Week 2 (Day 8 – Day 14): If tolerated, increase dose to two placebo capsules in the morning and one placebo capsule in the afternoon • Week 3 (Day 15 – Day 17): One placebo capsule in the morning • Week 3 (Day 18 – Day 21): No treatment 
Period 2 (AXS-12):
 
 • Week 4 (Day 22 – Day 28) [REDACTED] over-encapsulated reboxetine tablet in the morning and [REDACTED] over-encapsulated reboxetine tablet in the afternoon. • Week 5 (Day 29 – Day 35): If tolerated, increase dose to [REDACTED] over-encapsulated reboxetine tablets in the morning and [REDACTED] over-encapsulated reboxetine tablet in the afternoon. • Week 6 (Day 36 – Day 38): [REDACTED] over-encapsulated reboxetine tablet in the morning • Week 6 (Day 39 – 42): No treatment 
Over-encapsulated tablets of reboxetine or placebo capsule will be dosed twice daily. The first dose (Day 1) will be taken in the morning at the study site during the baseline visit. [REDACTED] [REDACTED] [REDACTED] will be assessed by counting the number of capsules dispensed and returned as compared to the expected capsules to have been consumed. Subjects who report <80% compliance with study drug may be withdrawn from study drug after consultation with the Sponsor.
 |
| 
STUDY DURATION
 | 
The duration of participation will be approximately 9 weeks as follows: Screening Period: up to 21 days Treatment Period 1: 3 weeks, including one week of down titration Treatment Period 2: 3 weeks, including one week of down titration
 |

| | |
|----------------------------------|---|
| 
CRITERIA FOR EVALUATION
 | 
Primary Efficacy Variable: The primary efficacy variable is the frequency of cataplexy attacks as self-reported in the Sleep and Symptom Daily Diary
 
Primary Endpoint: The primary efficacy endpoint is the change from Baseline to Week 2 of each treatment period in the frequency of cataplexy attacks as recorded in the Sleep and Symptom Daily Diary. Baseline will be calculated as the mean number of attacks during the 7 days prior to the study visit.
 
[REDACTED]
 
Secondary Efficacy Variables: Secondary efficacy variables will include:
 
• PGI-C• HAM-D• ESS• NSAQ• Ability to Concentrate item of the NSAQ• Safety variables: reports of treatment-emergent adverse events (TEAEs); clinical laboratory test results; vital sign measurements; and physical examination findings. |
| 
STATISTICAL METHODS
 | 
Analysis Populations: The following analysis populations are planned for this study:
 
• Modified Intent-to-Treat (mITT) Population: the mITT is the primary analysis population and will include data from all subjects who receive at least one dose of study medication and provide at least 1 post-dose efficacy assessment.• Safety Population: The Safety Population will include all subjects who receive at least 1 dose of the study medication. 
Membership in the analysis populations will be determined before unblinding.
 
The primary efficacy endpoint will be the change from Baseline to Week 2 of each treatment period in the number of cataplexy attacks as recorded in the Sleep and Symptom Daily Diary. Details of the statistical analysis will be provided in a Statistical Analysis Plan.
 |
| 
SAMPLE SIZE DETERMINATION
 | 
A sample size of 20 subjects was selected based on analysis of published results from a pilot open-label trial of reboxetine in narcoleptic subjects, and analyses of treatment effects of other agents studied in cataplexy.
 |
